17.1.1.1. Severity

Severity is classed as mild/ moderate/ severe (increasing severity). TEAEs starting after the first dose of study medication with a missing severity will be classified as severe. If a subject reports a TEAE more than once within that SOC/ PT, the AE with the worst case severity will be used in the corresponding severity summaries.

17.1.1.2. Relationship to Study Medication

Relationship, as indicated by the Investigator, is classed as "unrelated", "unlikely", "possible", "probable" (increasing severity of relationship), or "unknown". A "related" TEAE is defined as a TEAE with a relationship to study medication as a "possible" or "probable" relationship to study medication. TEAEs with a missing relationship to study medication will be regarded as a "probable" relationship to study medication. If a subject reports the same AE more than once within that SOC/ PT, the AE with the worst case relationship to study medication will be used in the corresponding relationship summaries.

Document: C:\Users\q832483\Documents\Insy CSR\Pending\Ready for QC\New folder\Statistical Analysis Plan.docx
Author: [REDACTED] Version Number: V1.0 Final
Version Date: 04APR2017

Template No: CS_TP_BS016 – Revision 3
Effective Date: 01May2012

Reference: CS_WI_BS005

17.1.2. TEAEs LEADING TO INTERRUPTION OF STUDY MEDICATION

TEAEs leading to interruption of study medication will be identified by a response of "Dose interrupted" for the "Action taken with study medication" question on the AE page of the eCRF. For TEAEs leading to interruption of study medication, summaries of incidence rates (frequencies and percentages) by SOC and PT will be prepared. Such TEAEs will also be listed separately.

17.1.3. TEAEs LEADING TO DISCONTINUATION OF STUDY MEDICATION

TEAEs leading to permanent discontinuation of study medication will be identified by a response of "Dose discontinued" for the "Action taken with study medication" question on the AE page of the eCRF. For TEAEs leading to discontinuation of study medication, summaries of incidence rates (frequencies and percentages) by SOC and PT will be prepared. Such TEAEs will also be listed separately.

17.1.4. SERIOUS ADVERSE EVENTS

Serious adverse events (SAEs) are those events recorded as "Serious" on the *Adverse Events* page of the (e)CRF. A summary of serious TEAEs by SOC and PT will be prepared. SAEs will also be listed separately.

17.1.5. ADVERSE EVENTS LEADING TO DEATH

TEAEs leading to Death are those events which are recorded as "Fatal" on the *Adverse Events* page of the eCRF. A summary of TEAEs leading to death by SOC and PT will be prepared. Such TEAEs will also be listed separately.

17.1.6. ADVERSE EVENTS OF SPECIAL INTEREST (AESIs)

AESIs identified in [Appendix 2](#) will be listed and summarized as follows:

- AESIs by SOC and PT
- AESIs by SOC, PT and relationship to study drug
- Related AESIs by SOC, PT and maximum severity

Two other events are of special interest and will be reported separately as follows:

- The relation between Somnolence event and the administration of Clobazam will be summarized.
- Subjects with Anemia events will be listed (values of hemoglobin, hematocrit and erythrocytes will be reported over time)

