1.1.4.3 Efficacy in Human Epilepsy

While efficacy is not a primary endpoint for this study (see Section 2.0), several preliminary studies of cannabidiol report reductions in seizure activity for a significant subset of subjects.

Cannabidiol was examined as an adjunctive therapy in 15 subjects with secondary generalized epilepsy with temporal focus who were refractory to conventional treatment.^{2,3} The 8 subjects randomized to the active arm received 200 to 300 mg/day of cannabidiol or placebo for up to 4.5 months in addition to previously established antiepileptic drugs (AEDs).^{2,58} Subjects tolerated cannabidiol well, with no signs of toxicity or serious side-effects. Four (4) of the 8 subjects receiving cannabidiol remained almost free of convulsive crises throughout the study and 3 others experienced partial improvement. The clinical condition of 7 subjects receiving placebo remained unchanged and 1 subject improved.

Parents of children with treatment-resistant epilepsy have sought cannabidiol-enriched *cannabis* for treatment.⁴ In a survey, these parents reported dosages of cannabidiol ranging from <0.5 to 28.6 mg/kg/day, as per results from medical *cannabis* testing facilities. Sixteen (16; 84%) of the 19 parents eligible to respond to the survey reported a reduction in their child's seizure frequency while taking cannabidiol-enriched *cannabis*. Of these, 2 (11%) reported complete seizure-freedom, 8 (42%) reported >80% reduction in seizure frequency, and 6 (32%) reported a 25% to 60% seizure reduction. Reported side-effects included fatigue and somnolence.

Realm Oil is an extract from a strain of *cannabis* known as Charlotte's Web and contains a cannabidiol:Δ⁹-THC ratio >20:1. Gedde and Maa⁵ reported on a small group of pediatric subjects diagnosed with various types of epilepsy who took Realm Oil for ≥3 months. Baseline seizure frequency for these subjects ranged from 5 to 2800 events per week. Eight (8; 73%) of these subjects reported a 95% to 100% reduction in seizure occurrence, 1 (9%) reported 75% reduction, and 2 (18%) reported 20% to 45% reduction.

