1.2 Pediatric Treatment-Resistant Seizure Disorders

The clinical manifestations of epilepsy are periodic, uncontrolled, convulsive seizures. The highest incidence of epilepsy in North America and Europe is in the first 12 months of life when 90 to 212 cases per 100,000 individuals are diagnosed. Children diagnosed with various types of epilepsy have an increased risk (23% to 34%) of behavioral and cognitive symptoms and comorbidities.⁶²

As recently reviewed,^{62,63} current interventions for pediatric epilepsy patients include the following:

- AEDs
 - The FDA has approved multiple medications (i.e. clonazepam, felbamate, lamotrigine, topiramate, rufinamide, and clobazam) for adjunctive use in pediatric epilepsy. Although not approved in the US, other AEDs that may be used in this population include stiripentol.
- Resective surgery for specific types of drug-resistant focal epilepsy (e.g., Rasmussen encephalitis and tuberous sclerosis complex)
- Ketogenic diet or low-glycemic index diet
- Vagus nerve stimulation (VNS).

Safety and tolerability issues with current AED therapies include the following:

- Valproic acid: weight gain or loss, nausea and vomiting, pancreatitis, liver failure, thrombocytopenia, fetal anomalies if used in pregnancy, polycystic ovarian syndrome (PCOS), and hair loss
- Clobazam: irritability, sedation, hypotonia, and drooling
- Topiramate: decreased appetite, weight loss, decreased sweating, slowing of verbal processing, kidney stones, acidosis, and glaucoma
- Levetiracetam: behavior and mood issues.

Additionally, some currently approved AEDs have specific contraindications. For example, clobazam is excluded as a therapy for patients with significant liver disease or acute narrow angle glaucoma. Some AEDs also carry specialized warnings (e.g., serious skin reactions with clobazam and lamotrigine).

In addition to the above tolerability issues, 10% to 40% of patients with epilepsy are treatment-resistant.^{64,65,66} The hallmark of treatment-resistance seizures is the failure of ≥ 2 AEDs to control them.⁶⁷ Patients diagnosed with LGS and DS are frequently treatment-resistant. These indications will be among those investigated in this study (among other treatment-resistant seizure disorders) and will also be examined in planned Phase 3 studies. Data from the current study will inform the dose of the investigational product to be examined in the Phase 3 studies.

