3.4 Selection of Study Population

The study will include subjects who completed activities through Day 11 in INS011-14-029 or Part A in INS011-15-054. The estimated maximum number of rollover subjects from these previous studies is as follows:

- INS011-14-029: 60 subjects
- INS011-15-054: 20 subjects

If all subjects are eligible for and elect to rollover into INS011-14-030, the population of this study will be a maximum of 80 subjects.

Each subject must satisfy all inclusion/exclusion criteria in Sections 3.4.1 and 3.4.2.

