6.5. STATISTICAL TESTS

No statistical inferential procedures will be performed for this study.

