Concentration data of CBD and 7-OH-CBD will be tabulated and summarized by CBD dose level (based on the daily dosing regimen, mg/kg/day, of CBD when the plasma sample is taken) at each collection time (scheduled week) using descriptive statistics (n, mean, SD, minimum, median, maximum, and percent coefficient of variation). In addition, dose-normalized concentrations of CBD and 7-OH-CBD will be tabulated and summarized by clobazam flag

Pharmacokinetic Statistical Analysis Plan
Insy Clinical Trial Protocol INS011-14-030

(yes/no) at each collection time (scheduled week) using descriptive statistics. CBD and 7-OH-CBD concentration-time data for subjects continuing on study medication as part of the Expanded Access Program will be summarized in a secondary set of tables and figures.

Concentration data of clobazam and norclobazam will be stratified by clobazam flag (yes/no), tabulated, and summarized using descriptive statistics.

In the data tabulation and summarization, concentrations below the lower limit of quantitation (BLQ) will be set to zero.

Plots of mean concentration-time for CBD and 7-OH-CBD and dose-normalized CBD and 7-OH-CBD will be created by CBD dose level, with and without stratification by clobazam (yes/no). Plots of concentration-time data for CBD and 7-OH-CBD for individual subjects will be created; since the dose level may vary during the study, the dose level at a given sample time will be labeled or foot-noted (if possible) in the figure. Plots for clobazam and norclobazam will be stratified by subjects on clobazam therapy (yes/no).

Pharmacokinetic Calculations

The metabolite-to-parent ratio (MRCtrough) will be calculated using concentrations of 7-OH CBD (metabolite) and CBD (parent) at each Visit, starting with the first trough sample obtained and through the remaining visits. If either CBD or 7-OH CBD concentration is not reportable or BLQ, MRCtrough will be reported as "not applicable". MRCtrough for clobazam will be calculated using the same methodology.

To assess the degree of accumulation during long-term BID administration of cannabidiol oral solution after 1 month treatment (Visit 5), an accumulation ratio (RCtrough) will be estimated using the dose-normalized trough plasma concentrations of CBD and 7-OH-CBD at each Visit, according to:

$$RCtrough = \text{Conc}/D(n^{\text{th}} \text{ visit dose})/\text{Conc}/D(5^{\text{th}} \text{ visit dose}),$$

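### The only planned adverse-event summary by clobazam use counts the single term Somnolence and leaves out Sedation, Lethargy and Hypersomnia, so a clobazam association may be missed or understated

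*SAP*

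**What the plan says.** SAP 17.1.6 sets out the tables for adverse events of special interest, for example "AESIs by SOC, PT and relationship to study drug". It then singles out two events for separate reporting, of which one is the point here: "The relation between Somnolence event and the administration of Clobazam will be summarized". The section does not define a grouped event or say what counts as receiving clobazam.

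SAP Appendix 2 lists Somnolence, Sedation, Lethargy, Hypersomnia and Fatigue as five separate preferred terms of special interest.

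Protocol 1.2, on the tolerability of existing antiepileptic drugs, has the entry "Clobazam: irritability, sedation, hypotonia, and drooling". Protocol 1.1.4.3, on a parent survey of cannabidiol-enriched cannabis, says: "Reported side-effects included fatigue and somnolence".

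The Pharmacokinetic SAP also splits results by clobazam, but only for plasma levels: "dose-normalized concentrations of CBD and 7-OH-CBD will be tabulated and summarized by clobazam flag".

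On size and inference, Protocol 3.4 says that "the population of this study will be a maximum of 80 subjects", and SAP 6.5 says that "No statistical inferential procedures will be performed for this study".

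**The concern.** Protocol 6.1.1.1 asks sites to watch for more frequent or new side effects of background antiepileptic drugs, because cannabidiol may change their metabolism. For clobazam, the obvious clinical question is whether sedation-type events cluster in users. The SAP has one adverse-event table aimed at that question, and the table counts one of several neighbouring terms. It omits the term that the protocol itself uses for clobazam's effect.

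If a site writes that a child was sedated or lethargic and the event is coded accordingly, the child appears in the general tables but not in the clobazam comparison. With at most 80 subjects, moving a few children out of the count can change how the table reads.

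**Working it through.** **1. Is the gap filled elsewhere?** These are the planned outputs that could relate the omitted terms to clobazam:

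- SAP 17.1.1: treatment-emergent events by system organ class and preferred term, shown by age category. There is no clobazam split.
- SAP 17.1.6, other tables: by class, preferred term, relationship and severity. There is no clobazam split.
- SAP 17.1, follow-up period: by whether cannabidiol continues after the final visit. There is no clobazam split.
- Pharmacokinetic SAP: concentrations and ratios by clobazam yes/no. There are no adverse events.

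None fills the gap. Nor can the preferred-term rows be added up to give subjects with any sedation-type event, because one subject may appear in several rows.

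**2. What is certain.** The number of subjects with Somnolence cannot exceed the number with any of the four terms. The two are equal only if nobody is coded solely to Sedation, Lethargy or Hypersomnia.

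**3. What depends on coding.** The plan gives no figure to reproduce. Everything below is assumed except N = 80. Let p1 and p0 be the proportions of clobazam users and non-users with any of the four terms. Let f be the share of those subjects coded to Somnolence, the same in both groups. Then:

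- difference shown = f × (p1 − p0)
- risk ratio shown = (f × p1)/(f × p0) = p1/p0, unchanged
- 95% half-width = 1.96 × √[a(1 − a)/40 + b(1 − b)/40], with a = f × p1 and b = f × p0

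With 40 users, 40 non-users, p1 = 0.40 and p0 = 0.15:

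| f | Expected subjects | Difference | Half-width | Risk ratio |
|---|---|---|---|---|
| 1 (grouped row) | 16.0 vs 6.0 | 0.250 | 0.188 | 2.67 |
| 0.7 | 11.2 vs 4.2 | 0.175 | 0.168 | 2.67 |
| 0.5 | 8.0 vs 3.0 | 0.125 | 0.148 | 2.67 |
| 0.3 | 4.8 vs 1.8 | 0.075 | 0.119 | 2.67 |

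The difference shrinks faster than its half-width. At f = 0.5 the interval would include zero (0.125 − 0.148 = −0.023). For the grouped row it would not (0.250 − 0.188 = 0.062). With 24 users and 56 non-users, the corresponding pairs are 0.250 ± 0.217 and 0.125 ± 0.174. The intervals serve only as a yardstick, since the SAP plans no inference.

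**4. If coding is not proportional.** Here a subject has either Somnolence or one of the other terms, so the proportions add:

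| Assumed pattern (users vs non-users) | Somnolence only | Grouped |
|---|---|---|
| Effect sits in the omitted terms: Somnolence 10% vs 5%, others 30% vs 10% | difference 0.05, ratio 2.0 | 40% vs 15%: difference 0.25, ratio 2.67 |
| Omitted terms unrelated to clobazam: Somnolence 25% vs 5%, others 20% vs 20% | difference 0.20, ratio 5.0 | 45% vs 25%: difference 0.20, ratio 1.8 |

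In the first pattern the single-term table nearly loses the signal. In the second it gives the clearer contrast, and pooling dilutes it. The documents do not say which pattern is nearer the truth.

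**The case against.** **Under-detection is not shown.** A reader might infer that the clobazam association *is* under-detected. The documents do not support that. They give no event rates, coding split or clobazam share. Under proportional coding the risk ratio is untouched, and under the second pattern in the last table the single term does better. This objection stands in full, and it is why the conclusion says only that an association may be missed or understated.

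**The table is not the main evidence on the interaction.** A reader might also infer that it is, because the protocol measures clobazam levels only when there is a safety concern. The later Pharmacokinetic SAP drops that condition: it plans clobazam and norclobazam levels for patients on clobazam, and cannabidiol levels by clobazam use. This also stands. Concentrations, however, do not show whether sedation clusters in users.

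**Somnolence is a defensible choice.** Protocol 1.1.4.3 reports fatigue and somnolence with cannabidiol-enriched cannabis, and Protocol 1.2 describes clobazam as an existing drug, not its interaction with cannabidiol. That is a reason to keep the Somnolence row, but not to omit the others. It also supports a version that includes Fatigue.

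**Interchangeable wording is assumed.** The documents do not say that caregivers or sites use these terms for the same finding. It is plausible, but the size of the loss depends on it.

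**The harm is recoverable.** Events and concomitant medications will be listed, with antiepileptic drugs flagged, so a grouped count could be built later. The table templates mentioned in SAP 8 are not available and might define the event more broadly. This limits the harm. Even so, a grouping chosen after the data of an open-label study have been seen is less credible than one fixed beforehand.

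**Conclusion.** The gap is real and its consequence is possible, not demonstrated. Subjects coded only to Sedation, Lethargy or Hypersomnia are left out of the one planned adverse-event summary by clobazam use. Sedation-type events are under-counted there whenever such subjects exist.

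The effect on the association cannot be sized from the documents. In the assumed proportional case, with 30% to 70% coded to Somnolence, a difference of 25 points would show as 7.5 to 17.5 points with the ratio unchanged. Other coding patterns make the loss larger or reverse it. Clobazam use is not randomised and the analysis is descriptive, so the point concerns the clarity and completeness of one safety table, not the validity of the study. It is a modest change, worth making because it costs so little.

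**What to change.** In SAP 17.1.6:

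1. Keep the Somnolence row.
2. Add a grouped row for any of Somnolence, Sedation, Lethargy or Hypersomnia, each subject counted once. Add a second version that includes Fatigue.
3. Tabulate all rows by a fixed subject-level group, for example any clobazam use during the treatment period of this study against none, so that numerator and denominator refer to the same subjects. Clobazam use at event onset cannot define the groups: subjects without an event have no onset date, and Protocol 4.3 lets antiepileptic drugs start or stop during the study.
4. Show clobazam status at onset as a supportive listing, since under the fixed grouping an event before clobazam was started still counts for a user. Alternatively, use person-time on and off clobazam for subjects who switch.
5. While editing, correct the description of Somnolence and Anemia as additional to the Appendix 2 list, because both are already on it.

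The cost is a few SAP sentences, one group of terms already in Appendix 2 and one derived clobazam variable from the concomitant-medication page. No new data are needed. The downside is possible dilution when terms unrelated to clobazam are pooled, and comparison with the retained Somnolence row would show it.

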17.1.7. CTC GRADING FOR ADVERSE EVENTS

No CTC grading is required for this study.

Document: C:\Users\q832483\Documents\Insy CSR\Pending\Ready for QC\New folder\Statistical Analysis Plan.docx
Author: [REDACTED] Version Number: V1.0 Final
Version Date: 04APR2017

Template No: CS_TP_BS016 – Revision 3
Effective Date: 01May2012

Reference: CS_WI_BS005

17.2. DEATHS

If any subjects die during the study, as recorded on the “Death Details” page of the eCRF, the information will be summarized and listed.

Primary reason for death will also be summarized by CBD status for deaths observed during the Follow-up period. CBD status will be flagged in the listing.

17.3. LABORATORY EVALUATIONS

Results from the central laboratory will be included in the reporting of this study for Hematology, Serum Chemistry, and Urinalysis. A list of laboratory assessments to be included in the outputs is included in [Appendix 3](#).

Data will be provided and presented in Standard International (SI) units.

Quantitative laboratory measurements reported as “< X”, i.e. below the lower limit of quantification (BLQ), or “> X”, i.e. above the upper limit of quantification (ULQ), will be converted to X for the purpose of quantitative summaries, but will be presented as recorded, i.e. as “< X” or “> X” in the listings.

The following summaries will be provided for laboratory data:

- Actual and change from baseline results will be summarized by time point and age category (for quantitative measurements) using descriptive statistics
- Shift from baseline according to normal range criteria (for quantitative measurements and categorical measurements as described in [Section 17.3.1](#)) by time point and age category
- Proportion of subjects who develop clinical laboratory result abnormalities of interest as described in [Section 17.3.1](#)

Each laboratory result will be compared, separately, to the both baselines as defined [Section 6.2](#).

Each laboratory result measured at the Follow-up visit will also be summarized (as described above) by CBD status.

All laboratory data will be listed with abnormal values flagged.

Data from *Urine Pregnancy Test* and *Blood Draw for Plasma Level* eCRF page will also be listed.

